For each of the 4 co-primary efficacy endpoints, an analysis of covariance model will be used with treatment group, pooled center, and smoking status as factors, with baseline weight and baseline measurement as covariates. Pairwise comparisons between the active doses and placebo will be calculated based on least-squares mean contrasts using a 2-tailed 95% confidence interval (CI). For subjects in the efficacy analysis populations with missing primary efficacy endpoints, multiple imputation by fully conditional specification methods will be used. The imputation model will use subject demographics (age, sex, race, baseline weight, and smoking status) and baseline and post-baseline mean number and severity of vasomotor symptoms. Sensitivity analyses will be performed with other multiple imputation methods and mixed model for repeat measurements.

Since the study design requires the comparison of 7 active dose groups with placebo for 4 co-primary efficacy variables, a two-tier closed testing procedure will be used to control the family-wise error. A step-down testing procedure will be followed. The following testing order of doses will be employed:

- a. Placebo versus 90 mg BID (daily dose 180 mg),
- b. Placebo versus 60 mg BID (daily dose 120 mg),
- c. Placebo versus 120 mg QD (daily dose 120 mg),
- d. Placebo versus 30 mg BID (daily dose 60 mg),
- e. Placebo versus 60 mg QD (daily dose 60 mg),
- f. Placebo versus 15 mg BID (daily dose 30 mg), and
- g. Placebo versus 30 mg QD (daily dose 30 mg).

The 4 co-primary efficacy endpoints will be compared at each dose level. Only when ESN364 is proved to be significantly better than placebo at a 2-sided alpha level of 0.05 for all 4 co-primary efficacy endpoints will this dose level be claimed to be superior to placebo. A failure to prove the significance for 1 or more co-primary efficacy endpoints will lead to a failure to claim superiority to placebo at this dose level, and the other dose levels after this one in the sequence will not be tested.

The primary efficacy analysis will be based on the FAS. A supportive analysis will be carried out for the co-primary efficacy variables based on the PPAS to examine the impact of premature dropouts and/or major protocol deviations.

Secondary Efficacy Analysis: Efficacy will be further assessed based on the secondary endpoints described above using the FAS.

Safety Analysis

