5.2 Full Analysis Set (FAS)

The FAS comprises the subset of subjects from the SAF who received at least one dose of study drug, had a baseline and at least one post-baseline efficacy evaluation. The FAS will analyze patients as randomized, irrespective of the actual treatment received. The FAS will be used for summaries and primary analyses of efficacy data, as well as selected demographic and baseline characteristics.

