7.4 Analysis of Efficacy

7.4.1 Analysis of Primary Endpoints

7.4.1.1 Primary Analysis of Co-Primary Endpoints

The primary efficacy analysis will be based on the FAS.

The mean frequency and severity of moderate to severe vasomotor symptoms as well as change from baseline will be summarized by study week and for the last on treatment week. See Section [7.10.6](#) for study week and endpoint derivations. Weekly means will be plotted.

For each of the co-primary efficacy endpoints, an analysis of covariance (ANCOVA) model will be used with treatment group, pooled center, and smoking status (current vs. former/never) as factors, with baseline weight and baseline measurement as covariates. Pooled centers will be generated and documented prior to database lock. The algorithm for pooling centers can be found in Section [7.10.2](#). If the inclusion of pooled centers creates modeling problems, then dropping that factor will be considered.

Pairwise comparisons between the active doses and placebo will be calculated based on least-squares mean contrasts using a 2-tailed 95% confidence interval (CI).

For subjects in the efficacy analysis populations with missing primary efficacy endpoints, multiple imputation by fully conditional specification methods will be used. The multiple imputation model is specified in Section [7.10.1](#).

Since the study design requires the comparison of 7 active dose groups with placebo for 4 co-primary efficacy endpoints, a two-tier closed testing procedure will be used to control the

family-wise error rate. A step-down testing procedure will be followed. The following testing order of doses will be employed:

- a. Placebo versus 90 mg BID (daily dose 180 mg),
- b. Placebo versus 60 mg BID (daily dose 120 mg),
- c. Placebo versus 120 mg QD (daily dose 120 mg),
- d. Placebo versus 30 mg BID (daily dose 60 mg),
- e. Placebo versus 60 mg QD (daily dose 60 mg),
- f. Placebo versus 15 mg BID (daily dose 30 mg), and
- g. Placebo versus 30 mg QD (daily dose 30 mg).

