The 4 co-primary efficacy endpoints will be compared at each dose level. If all 4 co-primary efficacy endpoints are statistically significantly better than placebo at a 2-sided alpha level of 0.05 for a given dose this dose level will be considered superior to placebo. A failure to prove the significance for one or more co-primary efficacy endpoints will lead to a failure to demonstrate superiority to placebo at this dose level, and the other dose levels after this one in the sequence will not be tested. In this testing sequence, if one comparison failed to provide the significance at this dose level, the comparisons at other dose levels following this sequence will not be tested.

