7.4.1.2 Secondary Analysis of Co-Primary Endpoints

The primary analysis for each of the co-primary endpoints will be repeated using an ANCOVA model with treatment group as a factor and baseline measurement as a covariate.

A supportive analysis will be carried out for the co-primary efficacy endpoints based on the PPS to examine the impact of premature dropouts and/or major protocol deviations. The method used for this analysis will be identical to the primary analysis described in Section [7.4.1.1](#). The missing value imputation method for the early termination might not be applicable for the analysis on PPS since the analysis set only includes completed subjects. Week 4 analyses will be performed on PPS4, and the Week 12 analyses will be performed on PPS12.

An analysis of the primary efficacy variable by week will be conducted with mixed model for repeated measurements (MMRM) on FAS. This analysis will use a restricted maximum likelihood (REML)–based repeated-measures approach. The analyses will include the treatment group, week and smoking status (current vs. former/never) as factors and baseline measurement as a covariate, as well as an interaction of treatment by week and an interaction of baseline measurement by week. An unstructured covariance structure shared across treatment groups will be used to model the within-patient errors. The Kenward-Roger approximation will be used to estimate denominator degrees of freedom and adjust standard errors. The treatment difference will be estimated at all study weeks.

In addition, MCP-Mod analyses as described in the MCP-Mod SAP will be performed on co-primary endpoints.

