7.10 Handling of Missing Data, Outliers, Visit Windows, and Other Information

7.10.1 Missing Data

If there are no diary entries for a particular calendar day, and the patient reported receiving at least one morning dose of study medication or at least one evening dose of study medication on that day, the frequency of vasomotor symptoms will be imputed to 0; otherwise, the frequency of vasomotor symptoms will be considered missing.

If no vasomotor symptoms were recorded for the day, and the patient reported receiving at least one morning dose of study medication and at least one evening dose of study medication on that day, the severity will be 0.

Missing primary endpoints will be handled by multiple imputation for continuous variables, and non-responder imputation for binary variables.

For study drug compliance, the capsules returned will be imputed to 0 at the visit if no bottle was returned for a visit.

Multiple Imputation Method:

Multiple imputation will be used to impute missing data and will be implemented using SAS® PROC MI. Missing data may be the result of missing Week 4/Week 12 frequency/severity of vasomotor symptoms measurements or the result of patients discontinuing treatment prior to Week 4/Week 12. Missing at random will be assumed.

The imputation model will include the subject demographics (age [$<$ median, \geq median], race [white, non-white], baseline weight [$<$ median, \geq median], and smoking status), and baseline and post-baseline frequency/severity of vasomotor symptoms. Missing data will be imputed 100 times to generate 100 complete data sets. The seed will be 98765. The fully conditional specification method will be used. The 100 complete data sets will then be analyzed using the same analysis method as the one used to analyze the primary endpoint. See Section [7.4.1.1](#). The results from the 100 fitted models will be combined using SAS® PROC MIANALYZE.

If the model fails to converge, exclusion of subject demographics will be considered.

Safety Data Imputation:

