7.10.6.1 Efficacy Visit Windows

For the weeks on treatment (weeks prior to the follow-up period), the last day is always the last day of exposure to treatment.

The study week determination for the vasomotor symptoms data is based on the following:

Analysis study week	Actual assessment day
Baseline	7 non-missing days prior to D1
Week 1	D1 to D7
Week 2	D8 to D14
Week 3	D15 to D21
Week 4	D22 to D28
Week 5	D29 to D35
Week 6	D36 to D42
Week 7	D43 to D49
Week 8	D50 to D56
Week 9	D57 to D63
Week 10	D64 to D70
Week 11	D71 to D77
Week 12	D78 to D84 or last day of exposure to treatment, if this happened after day 84
Last on Treatment Week	Last 7 days of treatment
Follow-up Week 1	Day 1 FU – Day 7 FU ^
Follow-up Week 2	Day 8 FU – Day 14 FU ^
Follow-up Week 3	Day 15 FU – Day 21 FU ^

^ Day X FU is defined as last day of exposure to treatment + X

The assessment of a week will be derived if any information for 3 or more days was reported (morning dose, evening dose, or vasomotor symptom).

All other efficacy assessments, including those from unscheduled visits and regardless of visit label, will be allocated to analysis visits based on the table below:

CRF visit	Target day	Actual assessment day	Analysis visit
Visit 1	D-35	D-35 to D-1	Screening
Visit 2	D1	D1	Baseline
Visit 3	D29	D22 to D36	Week 4
Visit 4	D57	D50 to D64	Week 8
Visit 5	D85	D78 to Day 92	Week 12
End of treatment	Last dosing day	Closest observation to the date	EOT
Visit 6	D106	Last assessment after date of completion or termination of treatment period	Week 15 Follow-Up

The value which assessment day is the closest to the defined target day within these windows is used. If two values are equally close, the latter is used in the analysis.

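### The imputation model for all four co-primary endpoints omits treatment group; with 10% dropout equal across arms, Week 12 differences shrink by an estimated 1% to 6%, or up to about 9% if dropout is early

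*SAP*

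**What the plan says.** SAP 7.4.1.1 defines the primary analysis as an ANCOVA "with treatment group, pooled center, and smoking status (current vs. former/never) as factors, with baseline weight and baseline measurement as covariates". For missing endpoints it refers the reader elsewhere: "The multiple imputation model is specified in Section" 7.10.1.

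SAP 7.10.1 assumes missing at random and fixes the method (fully conditional specification), 100 imputations and the seed. The predictors it lists are age and baseline weight (each split at the median), race (white or non-white) "and smoking status), and baseline and post-baseline frequency/severity of vasomotor symptoms". The protocol synopsis has a similar list: "The imputation model will use subject demographics (age, sex, race, baseline weight, and smoking status) and baseline and post-baseline mean number and severity" of symptoms. Neither list contains treatment group, and no available text calls for imputation within arm. The only fallback, if the model does not converge, is to consider dropping the demographics.

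The step-down test runs on this imputed ANCOVA. At each dose all four endpoints must be significant: "A failure to prove the significance for one or more co-primary efficacy endpoints will lead to a failure to demonstrate superiority to placebo", and later doses are then not tested.

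**The concern.** An imputation model should contain every term that the analysis model estimates, and here it leaves out the term under test. A woman who stops early is given a Week 12 value from a regression fitted to placebo and seven active arms together. Her arm enters only through the weekly values she had already reported, and these carry only part of the Week 12 treatment effect. Missing at random does not cure this, because the imputation model must still represent the treatment effect.

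Diary entries made after stopping drug do not fill the gap. For on-treatment weeks, SAP 7.10.6.1 says that "the last day is always the last day of exposure to treatment", and a weekly value needs at least 3 reported days. Week 12 is Days 78 to 84, so a woman who stops before Day 80 has at most two usable days and no Week 12 value.

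At stake are the estimates used to choose a dose and the power of the confirmatory sequence. One missed endpoint ends testing of every later dose, and smaller effects are most likely near the end of the order. If dropout differs between arms, the bias could differ in size and direction between doses. The documents give no arm-specific rates from which to size that.

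**Working it through.** **The plan's own power figures.** Two-sample t-test, noncentral t, two-sided 5%, 40 per arm (SAP 4):

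| Endpoint (SD) | Difference | Plan | Recomputed |
|---|---|---|---|
| Frequency (5) | 3.3 / 3.5 / 4 / 4.5 / 5 | 83 / 87 / 94 / 97 / >99% | 83.0 / 87.1 / 94.2 / 97.8 / 99.3% |
| Severity (1) | 0.64 / 0.75 / 1 | 80 / 91 / >99% | 80.7 / 91.2 / 99.3% |

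These reproduce to within 1 point.

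**Inputs from the documents.** Eight equal arms; 10% premature discontinuation, the same allowance in every arm; SD 5 (frequency) and 1 (severity); the FAS requires that a subject "had a baseline and at least one post-baseline efficacy evaluation", so every dropout has at least one post-baseline week.

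**Assumptions (not in the documents).** The 10% is taken as the missing fraction. Between-person share of variance is 0.3 or 0.6, with the remainder AR(1) at 0.5 or 0.8. The effect is full at Week 1 or rises linearly to Week 4. The seven active arms are equally effective. The last observed week is uniform on 8-11 (late), 1-11 (spread) or 1-3 (early). All observed weeks are used as predictors.

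**Formula.** Regress Week 12 on baseline and Weeks 1 to k in the pooled data, without arm, with coefficients b. Let d_j be the true arm difference at week j. Then

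shrinkage = missing fraction × average over k of [1 − Σ b_j d_j / d_12].

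**One case in full.** Difference 4.0, SD 5, share 0.6, AR(1) 0.8, full effect at Week 1, last observed week 1.

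- Pooling adds (7/8)(1/8)(4.0²) = 1.75 to post-baseline variances and covariances.
- Variances: baseline 25; Week 1, 25 + 1.75 = 26.75. Their covariance is 25 × 0.92 = 23.
- Covariances with Week 12: baseline 15.69; Week 1, 15.86 + 1.75 = 17.61.
- Solving gives b = 0.105 (baseline) and 0.568 (Week 1).
- The baseline arm difference is 0, so the predicted difference is 0.568 × 4.0 = 2.27. The share lost is 1 − 0.568 = 0.432, and 10% × 0.432 = 4.3%.

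**Over the grid:**

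| Endpoint | Late | Spread | Early |
|---|---|---|---|
| Week 12 frequency, 4.0 | 1.2-3.6% | 2.5-5.9% | 4.0-8.7% |
| Same, per day | 0.05-0.15 | 0.10-0.24 | 0.16-0.35 |
| Week 12 severity, 0.64-0.75 | 1.3-3.8% | 2.6-6.1% | 4.1-8.8% |
| Week 4 frequency, 4.0 | 0 | 0.4-2.0% | 1.6-7.4% |

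Using frequency and severity together as predictors (correlation 0.3 or 0.6) gives 0.9-3.7%, 1.9-6.0% and 3.0-8.7% at Week 12. Other structures (compound symmetry 0.5-0.8, AR(1) 0.8-0.9 or mixtures, with immediate or exponential onset) gave 1.4-6.7% for spread dropout. By simulation under a selection of these structures, early dropout gave 3.4-9.5%.

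**Power for a fixed 3% to 6% loss**, one test, 44 per arm all counted as observed:

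| Difference | No loss | 3% loss | 6% loss |
|---|---|---|---|
| Frequency 3.3 | 86.5% | 84.4% | 82.1% |
| Frequency 4.0 | 96.0% | 94.9% | 93.7% |
| Frequency 5.0 | 99.6% | 99.4% | 99.2% |
| Severity 0.64 | 84.3% | 82.1% | 79.7% |

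**Trial-size simulation.** Week 12 frequency only, 8 × 44 subjects, 10% dropout, 30 imputations, ANCOVA with Rubin's rules, 1,400 trials per cell. Each data set was imputed with and without arm; the Monte Carlo error of the paired power difference is at most 0.25 points.

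- Difference 3.3, spread dropout: power 80.6-82.3% without arm against 82.7-84.2% with it, a loss of 0.5 to 3.1 points. Early: 1.6 to 5.1 points lost. Late: between 1.0 lost and 0.1 gained.
- Difference 4.0: spread 0.0 to 1.0 lost; early 0.3 to 2.3 lost; late no material change.
- With arm in the model, mean estimates were 3.25-3.34 (true 3.3) and 3.95-4.04 (true 4.0), so the added term removes the bias to within simulation error.

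**The case against.** The strongest reply is that the effect is small. It creates no false superiority claims when dropout is equal, it costs under 1 power point at the Phase 2a effect of 5.0, and at 4.0 with spread dropout it costs at most 1.0 point. The upper ends (5.9% spread, 8.7% early) occur only at the lowest correlation with slow onset, and nothing in the documents suggests that dropout clusters in the first weeks. All of this stands and limits the weight of the point.

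The 10% is a discontinuation rate, not a missing-data rate. SAP 7.10.1 also names missing Week 4 and Week 12 measurements as a source, which could raise it. Women who stop without post-baseline data leave the FAS, and those who stop on or after Day 80 can still have a Week 12 value, which could lower it. The shrinkage scales in proportion: 5% missing halves the figures above and 20% doubles them. The fixed-loss power table also starts above the plan's 40-completer basis, so the simulation is the fairer guide. Neither the joint power for four endpoints nor the full step-down sequence was computed.

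Other planned analyses help. The MMRM in SAP 7.4.1.2 does not share the flaw ("The analyses will include the treatment group, week and smoking status (current vs. former/never) as factors and baseline measurement as a covariate", plus treatment by week). MCP-Mod is planned. In the per-protocol analyses, subjects without the endpoint may be excluded, so imputation may not be needed. The protocol synopsis promises other imputation methods as sensitivity analyses, though the SAP does not detail them. None of these drives the step-down test.

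One could say the list leaves room for further terms, and the available text of protocol 10.2.1.1 breaks off within the imputation description. But the synopsis gives its list in full, and SAP 7.10.1 is the specification that 7.4.1.1 cites. A programmer following it would leave treatment out.

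**Conclusion.** The concern holds. As written, the primary analysis imputes all four co-primary endpoints at every dose from a model without the treatment term it then tests. With 10% missing equally in all arms, the Week 12 differences are understated by roughly 1% to 6%, and by up to about 9% if dropout is confined to the first weeks; the most adverse alternative structures go slightly higher. The omission and the direction of bias under equal dropout are certain from the text and the algebra. The size depends on the assumed correlations, onset and timing. The practical cost is negligible at 5.0 and modest at 3.3 (0.5 to 3.1 points with spread dropout, up to 5.1 with early dropout). It should be corrected because it is a specification error in the confirmatory analysis, it biases the estimates used for dose selection, and it is very cheap to remove.

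**What to change.** In SAP 7.10.1, add treatment group as a covariate in the fully conditional specification model, and state that it stays in if demographics are dropped for non-convergence. In the same edit, name the post-baseline weeks that enter the model. The text does not say, and if only Weeks 4 and 12 were used, a woman who stops before Week 4 would lose nearly all of her arm's effect under the present model.

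The cost is one added term in the SAP sentence and the PROC MI call, plus the list of weeks. No new data are needed. SAP Section 1 has the plan signed before hard lock and unblinding, so the change can be made without knowledge of results. The same correction in the protocol's description would keep the two documents aligned.

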7.10.2 Pooled Center

Approximately 352 subjects will be randomized at approximately 48 sites. When “center” is included as a factor in a statistical model, sites that have less than 10 FAS subjects in total will be identified and then combined for statistical analysis purposes according to the following algorithm:

- Step 1: Divide the sites into two groups with Group 1 including all sites that have at least 10 FAS subjects and Group 2 including all remaining sites. Sort each group in ascending order by total sample size and site number.
- Step 2: Starting at the top of the Group 2 list (i.e., the first site with the smallest total sample size), combine the minimum number of sites required to achieve a “pooled center” that has at least 10 FAS subjects in total. Continue forming “pooled centers” in this manner until all Group 2 sites have been grouped or it is no longer possible to form a “pooled center” with at least 10 FAS subjects in total.
- Step 3: If there is a site (or several sites) left after step 2, combine the site(s) with the last “pooled center” that is created. For the situation where no previous “pooled center” is created, combine the site(s) with the first site on the sorted Group 1 list.
- “Pooled center” will be assigned names PoolSite01, PoolSite02, etc. For sites not needing to be pooled, the original site name will be used such as Site001. For all sites that have been combined into pooled centers, the assigned pooled center will be used instead of the original site identification in all statistical models that include “center” as a factor. However, the original site identification will be used in all summaries of subject disposition or discontinuation by site and in all data listings.

7.10.3 Electronic and Paper Diaries

Subjects are to receive an electronic diary in which to record daily vasomotor symptoms during the study along with all home study drug intake. Paper diaries are to be used as back up to the electronic diary. In the case where there is an exact duplicate based on date and time between the electronic diary and the paper diary, the result from the electronic diary will be used. In the case where the date and/or time differs between electronic and paper diaries, results from both diaries will be used.

7.10.4 Last Dose Date

If the last dose date is missing from the eCRF, the last known dose date reported in the electronic diary will be used.

7.10.5 Outliers

All values will be included in the analyses.

7.10.6 Visit Windows

The study protocol gives the overall study schedule for these visits expressed as the number of days relative to Visit 2. Study Day will be calculated as date of visit/assessment – first dose date +1. There will be no Day 0. Visit 2 is scheduled to be Day 1 if the patient takes the first dose on Visit 2, and the day immediately prior to Visit 2 is Day -1.

Subjects will not be excluded from analyses due to the subject's failure to comply with the visit schedule.

If baseline is missing, the screening assessment can be used.

